3.1 Objectives and Endpoints

Table 1 Primary Study Objectives and Endpoints

Objectives	Endpoints and / or Estimands	Summary Measure(s)
Primary		
The primary objectives of the study are to evaluate the safety and PK of SC administration of CSL312 in the prophylactic treatment of pediatric subjects with C1-INH HAE.	Treatment-emergent adverse events (TEAEs)	Number of subjects, percentage of subjects, and number of events as well as the event rates per injection and per subject year
	PK parameters after SC administration of CSL312 at steady state: 
• C_{max}• C_{trough}• T_{max}	
• Mean (standard deviation [SD]) and geometric mean (geometric coefficient of variation percentage [CV%]) for all PK parameters except for T_{max}• Median (minimum, maximum) for T_{max}

Table 2 Secondary and Exploratory Study Objectives and Endpoints

Objectives	Endpoints and / or Estimands	Summary Measure(s)
Secondary		
The secondary objectives of this study are to evaluate efficacy, PD, and safety of CSL312 in the prophylactic treatment of pediatric subjects with C1-INH HAE.	
 Time-normalized number of HAE attacks Time-normalized number of HAE attacks treated with on-demand treatment Time-normalized number of moderate and / or severe HAE attacks Percentage reduction in the time-normalized number of HAE attacks 	
 The time-normalized number (per month and year) of HAE attacks, of HAE attacks treated with on-demand treatment, and of moderate and / or severe attacks on treatment, respectively The percentage reduction and the number of subjects experiencing at least $\geq 50\%$, $\geq 70\%$, $\geq 90\%$, or equal to 100% (attack-free) reduction in the time-normalized number of HAE attacks on treatment compared to their time-normalized number of HAE attacks documented in medical records
	
 Serious adverse events (SAEs) Deaths Related TEAEs TEAEs leading to study discontinuation TEAEs in each severity category Anti-CSL312 antibodies 	The number and percentage of subjects experiencing the specified safety events on treatment as well as the event rates per injection and per subject year

Objectives	Endpoints and / or Estimands	Summary Measure(s)
	
 Laboratory findings reported as adverse events (AEs) Adverse events of special interest (AESIs) (severe hypersensitivity including anaphylaxis) 	
	FXIIa-mediated kallikrein activity at scheduled time points	Descriptive summaries by nominal time point and the percentage of Baseline value
Exploratory		
The exploratory objective of the study is to further evaluate the PD effects of CSL312.	FXII concentration at scheduled time points	Descriptive summaries by nominal time point

C_{max} = maximum plasma concentration; C_{trough} = trough plasma concentration; C1-INH = C1-esterase inhibitor; FXIIa = activated factor XII; HAE = hereditary angioedema; PD=pharmacodynamic; PK = pharmacokinetic; SC = subcutaneous; T_{max} = time to reach maximum plasma concentration.

3.1.1 Primary Study Hypotheses

Not applicable. The study is a single-arm, open-label study, and the primary endpoint of the study is not an efficacy endpoint.

3.2 Study Treatments

Eligible subjects will be assigned to open-label CSL312 with a dosing regimen dependent on their age at the time of consent as follows:

- 2 to 5 years of age: 100 mg Q2M SC administration
- 6 to 11 years of age: 100 mg Q1M SC administration

If a subject turns 6 years of age during the study, the dose regimen will remain unchanged, and the subject will be analyzed in the age group according to the subject's age at the time of consent.

3.3 Randomization Procedures and Blinding

Not applicable. This is a single-arm open-label study with no randomization.

3.4 Determination of the Sample Size

No formal sample size calculation is made, and the sample size is not based on formal statistical considerations. This study will enroll a prespecified number of subjects as agreed with health authorities. See [Section 5.2](#) for definition of "enrolled".

3.5 Planned Interim Analyses

No formal interim analyses or sample size re-estimation are planned for this study.

3.5.1 Independent Data Monitoring Committee

An Independent Data Monitoring Committee (IDMC) will be established to monitor the efficacy and safety data generated during the study. The IDMC will consist of independent clinical specialists in HAE, who also have experience in clinical trials. The IDMC will review accumulating data from the ongoing study. Based on these reviews, the IDMC will advise on the further conduct of the study. No success or futility thresholds will be set for the IDMC reviews. The Sponsor will continue the study unless a safety issue is confirmed that warrants study termination. The composition, activities, analyses, responsibilities, and timing of meetings of the IDMC will be described in the IDMC charter.

The following outputs are planned for IDMC meeting #2:

1. Tables:
 - i. Demographic Characteristics
 - ii. HAE History
 - iii. Time-normalized Number of HAE Attacks During Various Time Windows of the Treatment Period
 - iv. Analysis of Responders
 - v. Overview of Treatment-emergent Adverse Events
 - vi. Overview of Serious Treatment-emergent Adverse Events
 - vii. Treatment-emergent Adverse Events by System Organ Class and Preferred Term

2. Figures:

- i. Subject Profiles for Study Participation, HAE Attacks by Severity, and On-demand Treatment

3. Listings:

- i. HAE Attacks – Investigator Reported
- ii. Derived Efficacy Variables: Time-normalized Number of HAE Attacks and Percent Reduction
- iii. Treatment-emergent Adverse Events

The IDMC mock TLF shells are provided in a separate supporting document.

In subsequent IDMC meetings, outputs may be added or removed including PK concentration listings and summaries.

4 Changes from the Protocol Planned Analyses

No changes to the analyses as presented in the study protocol are currently planned. Any changes in the planned analysis will be described in a new version of the SAP or in the CSR.

5 Study Analysis Sets

5.1 Screened Analysis Set

The Screened Analysis Set consists of all subjects who provided written informed consent / assent.

5.2 Enrolled Analysis Set

The Enrolled Analysis Set consists of all subjects in the Screened Analysis Set who were enrolled into the study. Subjects are considered "enrolled" in the study when they, or their legally authorized representative, has agreed to participate in the study after completing the informed consent process and Screening. Potential subjects who are screened to determine their eligibility but fail Screening or do not meet all the eligibility criteria, are not considered enrolled.

5.3 Safety Analysis Set

The Safety Analysis Set comprises all subjects in the Enrolled Analysis Set who received at least 1 dose of investigational product (IP). The Safety Analysis Set will be analyzed using the treatment that the subject actually received.

5.4 Per-protocol Analysis Set

The Per-protocol (PP) Analysis Set consists of all subjects in the Enrolled Analysis Set with no major protocol deviation potentially affecting the primary endpoint(s). Protocol deviations resulting in exclusion from the PP Analysis Set will be documented in the planned analysis review meeting (PARM) report before DBL. The PP Analysis Set will be analyzed using the treatment to which the subject was assigned regardless of the treatment that the subject actually received.

5.5 Pharmacokinetic Analysis Set

The PK Analysis Set consists of all subjects in the Safety Analysis Set for whom there is at least 1 quantifiable PK concentration of CSL312 after administration.

5.6 Pharmacodynamic Analysis Set

The PD Analysis Set consists of all subjects in the Safety Analysis Set for whom at least one PD measurement was obtained.

6 General Considerations

All analyses will be done by dosing regimen (100 mg Q1M and 100 mg Q2M) and overall (if not stated otherwise).

Datasets will be created according to Clinical Data Interchange Standards Consortium (CDISC) standards. Study data will be provided in Study Data Tabulation Model (SDTM) format. Analysis data will be provided in Analysis Data Model (ADaM) format.

SAS version 9.4 or higher will be used to perform all data analyses.

Summaries of continuous variables will be in terms of the number of observations, mean, SD, median, first quartile (Q1), third quartile (Q3), minimum and maximum. Other descriptive statistics (e.g., standard error, CV) may be reported when appropriate and will be described in the respective section. Categorical variables will be summarized using frequency counts and percentages. Analyses that use other descriptive statistics will have the specific descriptive statistics defined with the analysis in the applicable SAP section.

The by-subject listings will be sorted by dosing regimen, site-subject number, and by visit / date and time, or item number (if applicable).

Generally, only data of scheduled visits will be used in statistical summary tables; data from unscheduled visits will be included in the listings.

Actual, rather than planned, sampling time points will be used in the derivation of PK parameters and in the individual concentration-time plots and listing of plasma concentration data. The planned study visits will also be included in the listing. Planned sampling time points will be used in the descriptive summaries and in mean plots. Concentration-time data will also be listed according to actual sampling time points relative to previous injection.

7 Data Handling Conventions

7.1 Missing Data

Missing data occurs when any requested data are not provided, leading to blank fields on the collection instrument. These data will be indicated using a "blank" in subject listing displays. Answers such as "Not applicable" and "Not evaluable" are not considered to be missing data and should be displayed as such.

The primary safety endpoint is TEAEs and will not be missing. The monitoring of reported AEs is performed throughout the study. If inconsistencies are detected, queries will be generated. If a subject did not report TEAEs, the number of TEAEs will be 0.

As only descriptive statistics will be presented for all PK parameters (primary PK endpoints), missing data will not be imputed.

Missing efficacy data will not be imputed, as there is no formal statistical analysis being done. All subjects who drop out within the first 30 days of the treatment period will be regarded as missing for all efficacy analyses.

The details of handling missing data are presented in the corresponding sections of this SAP for the respective analyses (e.g., efficacy analyses, safety analyses).

7.2 General Derived Variables

7.2.1 Reference Dates and Study Days

Reference dates are used to assign study periods relative to treatment ([Section 7.4](#)).

- The efficacy reference date will be the Day 1 Visit date for subjects who did not receive treatment and the date of first IP for treated subjects and will be used to calculate study day for efficacy measures.

- The safety reference date will be the date of first IP and will be used to calculate study day for safety measures.
- The PK reference date will also be the date of first IP and will be used to calculate study day for PK measures.

The respective study day will be calculated as (date of interest - reference date) + 1 if the date of interest occurs on or after the reference date. If the date of interest occurs before the reference date, the study day will be calculated as (date of interest – reference date). There will be no study day 0.

7.2.2 Durations and Time to Event Data

Durations (e.g., the duration of an AE) are calculated in days as:

- event end date – event start date + 1, if end time or start time is not available.
- event end date / time – event start date / time, if both end time and start time are available.

Thus, there will be no duration of 0 if end time or start time are not available. If an AE has missing or partially missing start or end date, no duration will be calculated.

For elapsed time (e.g., the time to event), use:

- event date / time – reference date /time, (if time available).

Thus, an event which happens on the same date as the reference date will have an elapsed time of 0 if event time or reference time are not available.

To transform durations or elapsed times, which are calculated in days into weeks, the number of days will be divided by 7; to report in months, the number of days will be divided by 30.4375; to report in years, the number of days will be divided by 365.25. These algorithms return decimal numbers and ignore the actual number of days in the months or years (the calendar days) between start date and stop date. The "year" used in these algorithms is 365.25 days long, and the "month" is one twelfth of that year.

7.2.3 Baseline Definition

Baseline is defined as the most recent, non-missing value before the first IP administration (including unscheduled visits) for all assessments unless otherwise stated. For weight, the assessment on Visit Day 1, if available, will be used as Baseline even if it was taken after the first administration of IP. Assessments of weight after Visit Day 1 will not qualify as Baseline value.

7.2.4 Change from Baseline

Change from Baseline is calculated as:

- visit value – Baseline value.

Percentage change from Baseline is calculated as:

- (change from Baseline / Baseline value) * 100.

Percentage Baseline value is calculated as:

- (visit value / Baseline value) * 100.

If either the Baseline or visit value is missing, the change from Baseline, the percentage change from Baseline and the percentage Baseline value is also missing.

7.2.5 Multiple Assessments

All data will be reported according to the nominal visit date for which they were reported (that is, no visit windows will be applied during dataset creation and the visit will not be re-allocated if the actual visit date deviates from the planned date according to the visit schedule in the protocol). Unscheduled data will not be included in by-visit summaries, but may contribute to the Baseline value, the End of Study (EoS) value, or best/worst case value (e.g., shift tables) and will appear in listings.

If a laboratory sample was repeated due to technical problems the results from the valid sample(s) for this visit will be used in the analysis. If a laboratory sample was repeated as safety follow-up to monitor abnormal values of the initial sample, the initial sample (revealing the abnormal values) of this visit will be used in the analysis.

Data from all assessments (scheduled and unscheduled), including multiple assessments, will be included in listings.

7.2.6 Actual Treatment

All subjects will receive 100 mg CSL312. The subjects' actual dosing regimen is determined by the subject's age at time of consent and will be checked against the exposure data in the eCRF including the actual administered vial numbers. If a subject receives a dosing regimen that is different from the planned regimen for the entire time of treatment, then the actual dosing regimen will be considered the dosing regimen actually received. In case of other deviations from planned treatment, an evaluation of the case, final treatment assignment, and documentation of the decision will be done before DBL during the PARM.

7.3 Stratification

Not applicable.

7.4 Study Periods and Time Windows Relative to Treatment

The following definitions for the periods of efficacy and safety will be used to define the durations used in the denominator of the time-normalized endpoints and safety endpoints such as exposure and subject-years. The definitions of the time windows will be used in the efficacy analyses and the analysis of TEAEs.

Table 3 Overview of Study Periods and Time Windows

Study Period	Start Date	End Date	Duration
Screening Period	Informed Consent date	Day 1 Visit date - 1 if Informed Consent Date is before Day 1 Visit date. Informed Consent date if Informed Consent date is on Day 1 Visit date.	End Date - Start Date + 1 if Informed Consent Date is before Day 1 Visit date. 0 if Informed Consent date is on Day 1 Visit date.
Treatment Period/ Efficacy Evaluation Period	Day 1 Visit date or date of first IP if available	End of Treatment (EoT) Visit date or for premature discontinuations without the EoT Visit the last available visit or event date [whichever occurs later]. If the EoT Visit of a subject is delayed by more than the treatment time window relative to the last IP administration, EoT Visit date will be set to last IP administration + 30 days or + 60 days for Q1M or Q2M, respectively.	End Date - Start Date + 1
Follow-up Period if applicable	EoT Visit date + 1	Follow-up Visit or for premature discontinuations after the EoT Visit the last available visit or last event date [whichever occurs later]	End Date - Start Date + 1
Safety Evaluation Period	Date of first IP	Subjects who choose not to continue to receive CSL312 or another	End Date - Start Date + 1

Study Period	Start Date	End Date	Duration
		prophylactic treatment: Follow-up Visit or for premature discontinuations the last available visit or last event date [whichever occurs later]. Subjects who choose to continue to receive CSL312 or another prophylactic treatment: EoT Visit or for premature discontinuations without the EoT Visit the last available visit or last event date [whichever occurs later].	
Time Window	Start Date	End Date	Duration
Efficacy: Day 1 Until Day 31	Day 1 Visit date or date of first IP if available	Study day 31	End Date – Start Date + 1
Efficacy: First 6 Months	Day 1 Visit date or date of first IP if available	Month 6 (Day 181) Visit Date	End Date – Start Date + 1
Efficacy: Second 6 Months	Month 6 (Day 181) Visit Date + 1 day	Month 12 (Day 361) EoT Visit Date. If the EoT Visit of a subject is delayed by more than the treatment time window relative to the last IP administration, EoT Visit date will be set to last IP administration + 30 days or + 60 days for Q1M or Q2M, respectively.	End Date – Start Date + 1
Safety: First 3 Months	Date of first IP	EoT date if subjects discontinued or date of first IP + 90 if subjects is ongoing	End Date – Start Date + 1
Safety: Second 3 Months	End Date of previous 3- Months' Time Window + 1	EoT date if subjects discontinued or start date + 90 if subjects is ongoing	End Date – Start Date + 1
Safety: Third 3 Months	End Date of previous 3- Months' Time Window + 1	EoT date if subjects discontinued or start date + 90 if subjects is ongoing	End Date – Start Date + 1

Time Window	Start Date	End Date	Duration
Safety: Fourth 3 Months	End Date of previous 3-Months' Time Window + 1	EoT date if subjects discontinued or start date + 90 if subjects is ongoing	End Date – Start Date + 1
Safety: Fifth 3 Months (if applicable)	End Date of previous 3-Months' Time Window + 1	EoT date if subjects discontinued or start date + 90 if subjects is ongoing	End Date – Start Date + 1
...			

Note:

The first day of the Treatment Period may occur on the same day as the Screening Visit for subjects meeting the eligibility criteria for the study. In this case, the duration of the Screening Period is 0.

The Follow-up Visit is mandatory in this study unless a subject chooses to continue to receive CSL312 (and meet the criteria to participate in a post-study access program) or another prophylactic treatment. For these subjects, the Follow-up Period is not applicable.

The length of the month in the 3-Months' Safety time windows is set to 30 days.

8 Study Population

Unless otherwise stated, all tables and listings in this section will be presented by dosing regimen (100 mg Q2M and 100 mg Q1M) and overall.

Subjects who turn 6 years of age during the study will remain on their dosing regimen from study start and will be analyzed for the age group at their date of consent.

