## **7. SUBJECT WITHDRAWAL AND DISCONTINUATION OF INVESTIGATIONAL PRODUCT**

### **7.1. Discontinuation of Investigational Product**

Subjects may discontinue investigational product at any time at their own request, or at the discretion of the investigator or the sponsor for safety, behavioral, or administrative reasons.

Subjects who discontinue investigational product will remain in the study to complete follow-up activities or allow data collection as detailed in the Schedule of Activities ([Section 1.3](#)). Subjects discontinuing investigational product who decline further study procedures / visit participation will be withdrawn from the study (see [Section 7.2](#)).

Primary oversight during the conduct of the study will be the responsibility of the investigator. The investigator is responsible for evaluating the appropriateness of subjects to be enrolled in the study and for communicating any issues that may compromise subject safety with the sponsor to ensure appropriate action can be taken to protect subjects. Safety surveillance, medical safety assessment, and risk management will be conducted by the sponsor's Global Safety Committees as per Safety Processes at the sponsor. Additionally, an Independent Data Monitoring Committee (IDMC) will be established to monitor the efficacy and safety data generated during the study ([Section 10.1.8.1](#)). The IDMC will review accumulating data from the ongoing study. Based on these reviews, the IDMC will advise on the further conduct of the study.

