8.5 Study Population - Derived Variables

Derivation of BMI at Baseline

BMI will be calculated using the following formula:

$$\text{BMI (kg/m}^2\text{)} = \text{Weight (kg)} / [\text{Height (m)}]^2$$

using the height measured at Screening and the weight measured at Baseline (see [Section 7.2.3](#)). If weight at Baseline is not available, the BMI will be missing.

BMI at later visits will be derived based on the most recent assessment of height and weight at the respective visit.

9 Efficacy Analyses

The primary objective of the study is to evaluate the safety and PK of SC administration of CSL312 in the prophylactic treatment of pediatric subjects with C1-INH HAE. Thus, the primary endpoints of the study are a safety and PK endpoint and not an efficacy endpoint. Please see [Section 10.2.1](#) and [Section 11](#) for a description of the primary safety and PK endpoints, respectively, and corresponding analysis.

Subjects who turn 6 years of age during the study will remain on their dosing regimen from study start and will be analyzed in the age group according to the subject's age at the time of consent.

The efficacy endpoints will not be included in any efficacy summary if the subject's duration for the Treatment Period is less than 30 days, i.e., the subject discontinued within 30 days after the Day 1 Visit date or the date of first IP, if available. The reason why an endpoint is not included will be provided in the by-subject listing.

The efficacy endpoints will also be assessed over time for 6-months' time windows, with the first window starting at the Day 1 Visit date or the date of first IP, if available. Only subjects who completed the entire time window (i.e., completed Visit Month 6 and Visit Month 12,

respectively) – allowing for visit windows as per Schedule of Assessment in the protocol – will be included in the analysis of this time window.

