9.2.1 Secondary Efficacy Analysis

The secondary efficacy endpoints will be analyzed using the Enrolled Analysis Set (see [Section 5.2](#)). The endpoint "time-normalized number of HAE attacks" will also be analyzed using the PP Analysis Set (see [Section 5.4](#)). This will also be applied to the supplementary analysis of secondary endpoints.

Subjects / caregivers will enter HAE symptoms into their electronic Diary and the start and end date and time, the interference of HAE symptom(s) with daily activities, and location(s) of the HAE symptom(s). Investigator-reported HAE attacks will be based upon review of subject diaries, relevant interval medical history, and physician judgment. The investigator may ask clarifying questions to assist in his / her assessment of whether an HAE attack occurred. If an attack occurred, the investigator would record the attack in the eCRF, the start / end date, the attack location(s), and the severity of the attack based on the most severe symptoms.

For all analyses considering HAE attacks, only the HAE attacks confirmed and reported by the investigator on the eCRF 'HAE Attacks' will be used.

HAE attacks with a start date and time after the first IP administration through the EoT Visit date (or last available visit or event date [whichever is later] if no EoT Visit date is available) will be counted for the Treatment Period and will be included in the analyses of efficacy. If the EoT Visit of a subject is delayed by more than the treatment time window relative to the

last IP administration, HAE attacks with a start date and time after first IP administration through the date and time of the last IP administration + 30 or 60 days for Q1M or Q2M regimen, respectively, will be counted for the Treatment Period. For subjects not treated, start date for counting the HAE attacks will be the Day 1 Visit date. HAE attacks without start time will be counted only if they start after Day 1 or the day after the date of first IP.

HAE attacks will be listed, including start date / time, end date / time, time between start of the attack and end of the most recent preceding attack or Day 1 Visit /first IP administration (if no preceding attack), anatomical locations, severity, most recent actual CSL312 dose and dosing date and time, potential trigger, duration in hours and days, period in which the HAE attack occurred and how many and which on-demand medications were taken per HAE attack.

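### SAP Table 3 does not confine the 6-month efficacy windows to the Treatment Period, so a child who stops dosing early but keeps attending can get a diluted first-window rate and an invalid second window

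*SAP*

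**What the plan says.** The SAP pieces that interact are these.

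- **Role of Table 3 (SAP 7.4).** The period definitions "will be used to define the durations used in the denominator of the time-normalized endpoints". Each duration is end date − start date + 1.
- **Treatment Period end.** This is the EoT Visit. If that visit is late relative to the last dose, "EoT Visit date will be set to last IP administration + 30 days or + 60 days for Q1M or Q2M, respectively". A child with no EoT Visit ends at the last available visit or event, with no reset.
- **First 6 Months.** It runs from first dose to "Month 6 (Day 181) Visit Date", with no reference to the Treatment Period end.
- **Second 6 Months.** It starts at "Month 6 (Day 181) Visit Date + 1 day". Its end is given as "Month 12 (Day 361) EoT Visit Date. If the EoT Visit of a subject is delayed by more than the treatment time window relative"; in that event the same reset applies.
- **Attacks counted (SAP 9.2.1).** When the EoT Visit is late, attacks count only "through the date and time of the last IP administration + 30 or 60 days for Q1M or Q2M".
- **Inclusion in a window (SAP 9).** "Only subjects who completed the entire time window (i.e., completed Visit Month 6 and Visit Month 12", respectively, within the schedule's visit tolerance. The 30-day minimum applies to the whole Treatment Period, not to each window.
- **Stopping product (Protocol 7.1).** "Subjects who discontinue investigational product will remain in the study to complete follow-up activities or allow data collection", following the Schedule of Activities. SAP 8.1 says such children may stay in the study until the Follow-up Visit.

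SAP 9.2.1.5 calculates every secondary efficacy endpoint by 6-month window, and SAP 9.2.1 lists them by window.

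**The concern.** The reset moves the end of the Treatment Period and the end of the second window. It does not move the end of the first window or the start of the second. Inclusion depends on visits attended, so an off-drug child who attends passes the test. Two things can follow.

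1. The first-window denominator contains days on which an attack would not be counted, so the rate is too low.
2. The second window can end on or before the day preceding its start. No rule says what to do with a zero or negative duration.

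Where it occurs, dilution or a negative window flatters the treatment. The quantities exposed are the by-window attack rates, percentage reductions, responder classes and attack-free proportions, in a study of about 20 children split over two regimens.

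**Working it through.** **Inputs.** Month 6 Visit on Day 181 and Month 12/EoT Visit on Day 361, each ± 4 days (Protocol 1.3.1 and 1.3.2). Last planned dose at Month 11 for Q1M and Month 10 for Q2M, which on 30-day months are Day 331 and Day 301. Reset of + 30 or + 60 days (SAP Table 3).

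**Step 1: a full course.** Q1M: 331 + 30 = 361. Q2M: 301 + 60 = 361. The reset reproduces the stated Day 361. The windows are 181 − 1 + 1 = 181 days and 361 − 182 + 1 = 180 days, together the 361-day Treatment Period. For children who complete dosing, Table 3 is consistent.

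**Step 2: early stop, with the Month 6 Visit on Day 181 and an EoT Visit late enough to trigger the reset.** Let E = last dose day + 30 or + 60. Counted days in the first window are min(E, 181), over a denominator of 181. Second-window length is E − 182 + 1 = E − 181. That length matters only if the Month 12 visit is also attended.

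| Regimen, last dose | E | First window: counted/181 | Second window (days) |
|---|---|---|---|
| Q1M, Day 61 | 91 | 0.50 | −90 |
| Q1M, Day 91 | 121 | 0.67 | −60 |
| Q1M, Day 121 | 151 | 0.83 | −30 |
| Q1M, Day 151 | 181 | 1.00 | 0 |
| Q2M, Day 61 | 121 | 0.67 | −60 |
| Q2M, Day 121 | 181 | 1.00 | 0 |

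So dilution and a negative second window nominally need a last dose before Month 5 for Q1M or before Month 4 for Q2M. With the Month 6 Visit on Day 177 or 185, the two zero-length rows become + 4 or − 4 days, and the Q1M Day 121 ratio becomes 0.85 or 0.82.

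**Step 3: effect on the first-window reduction.** Rate per month = attacks/days × 30.4375. Assume 2 counted attacks and a history of 6 in 6 months, that is 1 per month.

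- As written, for either last dose below: 2/181 × 30.4375 = 0.336, a 66.4% reduction.
- Capped, Q1M last dose Day 91: 2/121 × 30.4375 = 0.503, a 49.7% reduction. The uncapped window moves the child across the 50% responder line.
- Capped, Q1M last dose Day 121: 2/151 × 30.4375 = 0.403, a 59.7% reduction. The child is a responder either way.

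**Step 4: scoring the second window.** With a negative length, 0 attacks divided by (say) −30 days is a rate of 0, so 100 × (1 − 0) = 100% reduction: a responder at every threshold and attack-free. With zero length, 0/0 is undefined.

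**Step 5: effect on a percentage.** If a proportion p of the other n − 1 children is attack-free, adding one spurious case changes it by (p(n − 1) + 1)/n − p = (1 − p)/n. At an assumed p of 60%, that is 0.4/15 = 2.7 points at n = 15 and 0.4/5 = 8 points at n = 5. With assumed counts, 12/19 (63.2%) becomes 13/20 (65.0%). The ceiling of 1/n (6.7 points at n = 15, 20 at n = 5) is reached only if no other child is attack-free.

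**The case against.** The strongest reply is that the visit schedule largely closes this path. The Follow-up Visit, which is the final visit, falls 3 months after the last dose. Taking 3 months as 90 days, a last dose on Day 61, 91, 121 or 151 puts it near Day 151, 181, 211 or 241, well before Day 361. SAP 8.1 has children who stop treatment staying until that visit. On this path there is no Month 12 visit, the completion rule removes the child from the second window, and a child last dosed on Day 61 leaves before Month 6 and enters neither window. A window that ends before it starts could hardly be called completed, and the exposure and compliance listings reviewed before database lock might expose it. The windows are supplementary, the primary endpoints are safety and PK, and no test is planned.

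Much of this stands, and it makes the second-window failure uncertain. It does not remove the defect. Protocol 7.1 allows continued data collection under the schedule, where EoT is at Month 12, and Protocol 7.2 ties early EoT assessments to withdrawal from the study, not to stopping product. The SAP defines completing a window by visits. Even on the short path, a Q1M child last dosed on Day 121 can attend Month 6 before a Follow-up Visit near Day 211. If an EoT Visit is also recorded at about Day 151, or later and so reset, the first window still has 151 counted days over 181.

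**Conclusion.** The window definitions are wrong as written, in a limited case. The first-window dilution is the firmer part: it needs an early stop, attendance at Month 6, and a Treatment Period that ends (by EoT Visit or reset) before that visit. It also assumes that the SAP 9.2.1 cut-off governs window counts, which the SAP implies but does not state. If later attacks were counted instead, the first window would mix in off-treatment time. The negative second window additionally needs a Month 12/EoT visit by an off-drug child.

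A reader might infer more than the documents support:

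- That early stoppers will generally appear as sustained responders. The timing of the Follow-up Visit makes attendance to Month 12 doubtful.
- That every collapsed window scores as attack-free. At zero length (nominally Q1M last dose at Month 5, Q2M at Month 4) the rate is undefined.
- That one child shifts a percentage by 1/n. That is the ceiling; (1 − p)/n is the expected size.
- That the main efficacy results are biased. Whole-period rates use the reset end date for both numerator and denominator and are unaffected.

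The point is worth correcting before database lock because the rule is wrong and the repair is small, not because a large distortion is likely.

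**What to change.** In SAP Table 3:

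- End First 6 Months at the earlier of the Month 6 Visit date and the Treatment Period end date as reset.
- Form Second 6 Months only if the Treatment Period end date as reset is after the Month 6 Visit date.

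In SAP 9 and 9.2.1:

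- Apply the completed-window rule to the Treatment Period as reset, keeping the visit tolerance, rather than to attendance alone.
- State that attacks are counted only between the same dates that form the window's denominator.

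This works whether or not off-drug children attend to Month 12, so it need not wait for Protocol 7.1 and the Follow-up timing to be reconciled. The cost is a few lines of SAP text and programming, with slightly fewer children in the second window and, if the completion rule is applied strictly, in the first. Nothing changes for children who complete dosing.
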